3.1.3. Safety Analysis Set

The safety analysis set will include all patients in the DS group who receive at least 1 dose of IMP and all patients in the SoC group. In the safety analysis set, treatment will be assigned based on the treatment patients actually received, regardless of the treatment to which they were randomized, unless otherwise specified. This analysis set will be used for all safety analyses.

4. GENERAL ISSUES FOR DATA ANALYSIS

4.1. General

Descriptive statistics for continuous variables include n, mean, standard deviation (SD), standard error (SE), median, minimum, and maximum. Descriptive statistics for categorical variables include patient counts and percentages, missing category will be displayed as appropriate.

Treatment dates are defined as follows:

- Treatment start date: date of randomization/the screening/baseline visit date.
- Treatment end date: the end of treatment/early termination (ET) visit date. If the end of treatment/ET date is missing then the last contact date will be used.

4.2. Specification of Baseline Values

Baseline is the data observed at that screening/baseline visit, unless otherwise specified.

4.3. Handling Withdrawals and Missing Data

For the primary endpoint, patients who discontinue early due to technology failure, disliking the digital platform, disease worsening, adverse experience or disliking the IMP will be counted as treatment failures. For those who discontinue early not to these reasons, the ACT value assessed at ET visit will be used. Those who discontinue early and do not have an ET visit will be counted as treatment failures.

For the SUS items 1, 3, 5, 7, and 9, if response to 1 item is missing, the missing item will be replaced by the average of the remaining 4 responses. For items 2, 4, 6, 8, and 10, if response to 1 item is missing, the missing item will be replaced by the average of the remaining 4 responses. If response to 2 or more of items 1, 3, 5, 7, and 9 are missing, or 2 or more of items 2, 4, 6, 8, and 10 are missing, the overall SUS score will be set to missing.

For the BMQ subscales, if response to 1 item within a subscale is missing, the missing response will be replaced with the average of the remaining responses within the subscale. If response to 2 or more items within a subscale are missing, the missing responses will not be replaced and the subscale score will be set to missing.

For the BIPQ cognitive subscale, if response to 1 item within the subscale is missing, the missing response will be replaced with the average of the remaining responses within the subscale. If response to 2 or more items within the subscale is missing, the missing responses will not be replaced and the subscale score will be set to missing. For the emotional subscale, if 1 of the responses is missing then the subscale will be set to missing.

For an incomplete mini-AQLQ, the overall score for a particular visit will not be calculated if 1 or more responses are missing; total scores for the domains will be regarded as missing if 1 or more item will be incomplete.

4.4. Study Days and Visits

Study days are numbered relative to the treatment start date (ie, ..., -2, -1, 1, 2, ...; with day 1 being the treatment start date and day -1 being the day before the treatment start date).

Weeks are defined in 7-day intervals (days 1 to 7, 8 to 14, ..., 78 to 84). Day 1 is defined as the treatment start date (i.e., date of randomization/Visit 1 visit date).

By-visit (or by-week) summaries will include baseline, and the end of treatment and ET visits. The ET visit will be summarized as a separate visit.

5. STUDY POPULATION

5.1. General

The ITT analysis set will be used for all study population summaries, unless otherwise specified. Summaries will be presented by treatment group and for all patients.

5.2. Patient Disposition

Patients screened and screened but not randomized (with reason not randomized) will be summarized only for all patients using patient counts. Patients in the ITT analysis set, ITT analysis set who did not attempt to download the App, ITT analysis set who did not use the inhaler, safety analysis set, and mITT analysis set, patients who completed and withdrew from treatment (with reason for withdrawing), and patients who completed and withdrew from the study (with reason for withdrawal) will be summarized using descriptive statistics. The summary will be based on all patients. The denominator for calculating the percentages will be the number of patients in the ITT analysis set.

5.3. Demographics and Baseline Characteristics

The continuous variables of patient age, weight, height, and body mass index (BMI) will be summarized using descriptive statistics. The categorical variables of subject sex, race, and ethnicity will be summarized using descriptive statistics for each category. Missing categories will be presented if necessary.

5.4. Medical History

All medical history will be coded using the Medical Dictionary for Regulatory Activities (MedDRA). The incidence of medical history abnormalities will be summarized using descriptive statistics by system organ class (SOC) and preferred term. Patients are counted only once in each SOC category, and only once in each preferred term category.

5.5. Prior Therapy and Medication

Any prior therapy or medication a patient is taking at the screening/baseline visit will be recorded on the CRF. All prior therapies and medications will be coded using the World Health Organization (WHO) drug dictionary (WHO Drug).

The incidence of prior therapies and medications will be summarized using descriptive statistics by therapeutic class and preferred term. Patients are counted only once in each therapeutic class category, and only once in each preferred term category. Prior therapies and medications will include all medications taken and therapies administered before the treatment start date.

5.6. Study Protocol Deviations

Data from patients with any important protocol deviations during the study will be summarized overall and for each category using descriptive statistics.

6. DATA ANALYSIS

6.1. General

The efficacy of the drug product will not be evaluated in this study. The focus of this study is the engagement of the patient with the FS eMDPI DS and Albuterol eMDPI DS.

The mITT analysis sets will be used for all data analyses, unless otherwise specified. Summaries will be presented by treatment group, as randomized.

6.2. Primary Endpoint and Analysis

6.2.1. Definition

The ACT is a simple, patient-completed tool used for the assessment of overall asthma control. The 5 items included in the ACT assess daytime and nighttime asthma symptoms, use of rescue medication, and impact of asthma on daily functioning. Each item in the ACT is scored on a 5-point scale, with summation of all items providing scores ranging from 5 to 25. The scores span the continuum of poor control of asthma (score of 5) to complete control of asthma (score of 25), with a cutoff score of 19 and below indicating patients with poorly controlled asthma ([Schatz et al 2006](#)).

The primary endpoint is the proportion of patients for the DS and SoC groups reaching well-controlled asthma as defined by an ACT score of greater than or equal to 20, or a clinically important improvement in asthma control as defined by an increase of at least 3 units on the ACT score from baseline at the end of the 24-week treatment period (responder analysis of DS versus SoC group with responders defined by an ACT score of greater than or equal to 20 or an increase by greater than or equal to 3 units on the ACT score).

6.2.2. Primary Analysis

To analyze the primary variable, the following estimand framework will be used:

1. Population: The patients met all of the inclusion criteria and none of the exclusion criteria. The mITT analysis set will be the primary analysis set for the primary endpoint.
2. Variable: The primary endpoint will be a binary response variable at Week 24. A patient will be defined as a responder if the patient achieves an ACT score of greater than or equal to 20 or an increase of greater than or equal to 3 ACT units from baseline to Week 24. Otherwise, the patient will be defined as a nonresponder.
3. Intercurrent events: Treatment discontinuation due to an adverse event, lack of efficacy, technology failure, disliking the DS, disliking IMP, or other reasons. For those who discontinue the treatment before Week 24, no further data will be collected.
4. Population-level summary: The primary endpoint will be analyzed using a logistic model, where binary variable responder rate (Yes/No) will be modeled through logit link function, with baseline ACT score and treatment as explanatory factors. For those who discontinue the treatment before Week 24 due to technology failure, disliking the digital platform, adverse event related to IMP, or disliking the IMP, the patients will be defined as nonresponders; for those who discontinue early not due to these reasons, the response

at the ET visit will be used. The mean and 95% credible intervals of the response rates and OR from the posterior distributions will be calculated and presented. An informative prior will be assumed for the model coefficient for treatment and non-informative priors will be assumed for all other model coefficients.

Logistic regression model allowing for different response rates at enrolling investigational centers will be used for testing the hypothesis $H_0: \beta_1 = 0, H_1: \beta_1 > 0$ in the following model:

$$\ln\left(\frac{p_{ij}}{1-p_{ij}}\right) = \beta_0 + \beta_1 x_i + \beta_2 \text{baseline ACT value} + \text{Center}_j$$

where x_i = treatment group i , p_{ij} = response proportion of treatment group i at Center j, Center_j = random center effect of center j.

An informative prior of Beta [9.52, 11.88] for SoC group and a non-informative prior of Beta [0.5,0.5] for the DS group will be assumed. Those priors will be converted to Normal(mean = -0.231, var = 0.192) for β_0 and Normal(mean = 0.236, var = 9.912) for β_1 respectively. Estimates of mean response rate and corresponding 95% credible intervals for individual proportions, histograms of the posterior response rates, odds ratio with corresponding 95% credible intervals for DS versus SoC, and probability of ($\beta_1 > 0$) will be presented.

The SAS code for the primary analysis is as follows:

```

proc mcmc data = x nbi = 1000 nmc = 500000 thin = 20 seed = 159 outpost =
post1 monitor = (beta0-beta2 sigma2 beta1_gt0 pi pi0 pooled or)
statistics=(summary intervals);

parms beta0-beta2 0;
parms sigma2 1;

prior beta0 ~ normal (mean = -0.231, var = 0.192);
prior beta1 ~ normal (mean = 0.236, var = 9.912);
prior beta2 ~ normal (mean = 0, var = 1000);

prior sigma2 ~ igamma(shape = 0.001, scale = 0.001);
random b0 ~ normal (mean = 0, var = sigma2) subject = CENTER;

eta = beta0 + b0 + beta1*trt + beta2*y0;
pi = logistic(eta);
pi0 = logistic(beta0 + b0 + beta2*y0);
model count ~ binomial(n = total, p = pi);
array or[<# of sites>];

```

```
or [CENTER] = exp(b0 + beta1);  
pooled = exp(beta1);  
run;
```

where count = number of responders and total = number of patients.

In addition, summary statistics for the ACT score will be presented at baseline, visit 2, visit 3, and ET visits. ACT score values and changes from baseline to each visit will be summarized using descriptive statistics.

In addition, summary statistics for question 4 of the ACT will be presented at baseline, visit 2, visit 3, and ET visits. Question 4 of the ACT values and changes from baseline to each visit will be summarized using descriptive statistics.

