2.4. Sample Size and Power Considerations

The sample size was selected based on a Bayesian approach which allows for a range of underlying proportions rather than a fixed predefined value.

A total of 388 patients will be enrolled in the study (accounting for 10% early dropouts), 200 patients in the DS group and 150 patients in the SoC group, to be available for analysis. The sample size determination was made assuming binomial distribution for the primary endpoint. An informative prior for the SoC group (Beta [9.52, 11.88]) was selected to reflect the belief that the response rate of the SoC group is between 30% and 60% (most likely 45%, [Merchant 2016](#)) and the effect size between groups of 13% difference in response rates was considered clinically meaningful.

In addition, an informative prior for the SoC group was selected to ensure that the mean square error for the Bayes estimate from the informative prior is superior to the maximum likelihood estimate over a range of 30% and 60% of anticipated proportion for SoC group.

It should be noted that both power and Type 1 error are dependent on the absolute difference between the DS and the SoC groups as illustrated in [Figure 1](#) below by the operational characteristics calculated for the study design.

Figure 1: Operational Characteristics Calculated for the Study Design

MSE=maximum likelihood estimation; MSE=mean squared error

A non-informative prior (Beta [0.5,0.5]) for the DS group was selected due to lack of availability of data in the DS group.

With assumptions of response rates of 58% and 45% for the DS and SoC groups, respectively, sample size and randomization ratio, the probability of the posterior odds ratio (OR) of improvement (ie, $OR > 1$) for the DS group versus the SoC group of at least 0.95 is about 82%. This will ensure a 1-sided 5% Type 1 error rate and 78% power for an effect size for 13% difference between the groups provided that the proportion of responders in the SoC group is 45%.

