6.2.3. Sensitivity Analyses

Sensitivity analysis 1: This analysis will be performed by imputing missing ACT values using the multiple imputation (MI) method assuming missing at random (MAR). Those who discontinue the treatment before Week 24 due to technology failure, disliking the digital platform, adverse event related to IMP, or disliking the IMP will be considered having missing data. For those who discontinue early not due to these reasons, the ACT value assessed at the ET visit will be used. Those who discontinue early and do not have an ET visit will be considered having missing data.

The following steps will be performed for the analysis:

- Create complete datasets using imputation. The SAS code is as follows:

```
proc mi data = yy out = yy2 seed = 4192 n impute = 500 minimum = 5 maximum = 25;  
  class trt;  
  var trt actbase v2 v3;  
  monotone regpmm;  
run;
```
- For each dataset, the clinically important improvement in asthma control variable will be derived for each patient as defined in Section 6.2.1.
- Analyze each dataset using the model described below for the primary endpoint.

```
ods output Diffs = dif LSMeans = lsm;  
proc genmod data = indata;  
  by visit_imputation_;  
  class trt;  
  model y = trt actbase / dist = binomial;  
  lsmeans trt/pdiff cl diff exp;  
run;  
ods output close;
```

- The output datasets from the above analysis will contain odds ratio estimates from each of the 500 datasets. An overall estimate will be generated using PROC MIANALYZE . The SAS code is as following:

```
proc mianalyze data=zz;
  by visit;
  modeleffects estimate;
  stderr stderr;
  ods output paramestimates=or;
run;
```

Sensitivity analysis 2: The primary variable will be analyzed using the same method as defined in Section 6.2.2 excluding the random site effect from the logistic model. The SAS code will be used for the analysis:

```
proc mcmc data = x nbi = 1000 nmc = 500000 thin = 20 seed = 159 outpost =
post2 monitor = (beta0-beta2 sigma2 pi pi0 pooled or) statistics=(summary
intervals);

parms beta0-beta2 0;
prior beta0 ~ normal (mean = -0.231, var = 0.192);
prior beta1 ~ normal (mean = 0.236, var = 9.912);
prior beta2 ~ normal (mean = 0, var = 1000);
eta = beta0 + beta1*trt + beta2*y0;
pi = logistic(eta);
pi0 = logistic(beta0 + beta2*y0);
model count ~ binomial(n = total, p = pi);
pooled = exp(beta1);

run;
```

where count = number of responders and total = number of patients.

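### The prior for the overall SoC response rate sits on the intercept of a model with uncentred baseline ACT, so as printed it constrains response at an impossible ACT of 0 and can bias the primary odds ratio

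*SAP*

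**What the plan says.** SAP 2.4 says that the Beta(9.52, 11.88) prior "was selected to reflect the belief that the response rate of the SoC group is between 30% and 60" per cent, most likely 45%. It is a statement about the whole SoC arm, with no covariate. The same section says of the design: "This will ensure a 1-sided 5% Type 1 error rate and 78% power for an effect size for 13% difference between the groups", given 45% SoC responders.

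SAP 6.2.2 converts this prior to the normal scale and codes it as "prior beta0 ~ normal (mean = -0.231, var = 0.192"). The linear predictor is "eta = beta0 + b0 + beta1*trt + beta2*y0", where the displayed formula shows the covariate to be the baseline ACT value. The treatment coefficient has variance 9.912 and the ACT slope variance 1000. Nothing in the formula, code or text centres ACT.

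Item 4 of the same section, and item 4 of Protocol 9.5.4.1, say: "An informative prior will be assumed for the model coefficient for treatment and non-informative priors will be assumed for all other model coefficients". The code does the reverse.

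Sensitivity analysis 2 (SAP 6.2.3) keeps the same priors with "eta = beta0 + beta1*trt + beta2*y0". The Week 12 analysis in SAP 6.2.4 inherits the primary method by reference. Sensitivity analysis 1 uses "model y = trt actbase / dist = binomial", with no prior and no centre effect.

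**The concern.** In a model with an uncentred covariate, the intercept is the log-odds where that covariate equals zero. On the ACT, "Each item in the ACT is scored on a 5-point scale, with summation of all items providing scores ranging from 5 to 25", and Protocol 4.1 criterion d requires a score below 19. Baseline values therefore lie between 5 and 18, and the informative prior acts on a point outside the data.

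Two things follow. The intended information on the SoC rate is lost, because the vague slope prior swamps it at any real ACT score. And the line is tied to about 44% response at ACT 0. If the true SoC line does not pass near there, the fitted slope is distorted, the SoC level at observed scores is misfitted, and the nearly unconstrained treatment coefficient takes up the difference. Randomization does not protect against this, because the constraint acts on the SoC line alone.

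At stake are the primary odds ratio and the posterior probability that it exceeds 1. Both can move because of where a covariate's zero happens to lie.

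**Working it through.** **Inputs from the documents.** 200 DS and 150 SoC patients; 58% against 45% (odds ratio (0.58/0.42)/(0.45/0.55) = 1.69, log 0.523); success if the posterior probability of OR > 1 is at least 0.95 (SAP 2.4; SAP 6.2.2 states no threshold); priors as printed.

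**Assumptions.** Baseline ACT is Normal(14, 3) limited to 5–18, giving mean 13.6 and SD 2.6. The true slope ranges from -0.2 to +0.1 logits per ACT point. Centre variance is 0.10 or 0.25.

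**1. The plan's own figures.** Exact enumeration of the covariate-free beta-binomial design gives 81.7% with the informative SoC prior (stated: about 82%), with Type 1 error 4.6% at SoC 45%. With Beta(0.5, 0.5) in both arms, power is 77.9% and Type 1 error 5.0–5.1%, which matches the stated 78% and 5%. None of these comes from the model with baseline ACT. Under the informative prior the design's Type 1 error is 1.9% at SoC 30% and 9.3% at SoC 60%.

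**2. The prior conversion.** The logit of a Beta(9.52, 11.88) variable has mean -0.232 and variance 0.199; the SAP has -0.231 and 0.192. So the intercept prior is the overall SoC rate on the logit scale.

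**3. What it does as printed.** At ACT 0 the prior is -0.231 with SD √0.192 = 0.438, centred on 44%. At ACT 13.6 the slope prior alone contributes an SD of 13.6 × √1000 ≈ 430 logits, so nothing is said about the SoC rate there. Bias vanishes only when the slope is near (logit(SoC rate) + 0.231)/13.6:
- SoC 30%: (-0.847 + 0.231)/13.6 = -0.045
- SoC 45%: (-0.201 + 0.231)/13.6 = 0.00
- SoC 60%: (0.405 + 0.231)/13.6 = +0.047

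With slope -0.2 at SoC 45%, the true logit at ACT 0 is about -0.201 + 0.2 × 13.6 = 2.52. That is (2.52 + 0.231)/0.438 ≈ 6.3 prior SDs away.

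**4. Simulation without centre effects** (4,000 trials per setting; Monte Carlo SE about 0.3–0.6 points). Type 1 error:

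| SoC rate | Code | slope -0.2 | -0.1 | 0 | +0.1 |
|---|---|---|---|---|---|
| 45% | printed | 14.5% | 9.1% | 5.3% | 2.3% |
| 45% | centred | 4.0% | 4.5% | 4.7% | 4.5% |
| 30% | printed | 12.2% | 6.6% | 4.2% | 1.4% |
| 30% | centred | 1.3% | 1.7% | 1.9% | 1.4% |
| 60% | printed | 20.1% | 11.4% | 6.6% | 3.3% |
| 60% | centred | 11.4% | 9.2% | 9.7% | 10.3% |

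At SoC 45% the null bias in the log odds ratio as printed is +0.13, +0.07, 0.00 and -0.07. Power at 58% against 45% is 90.8%, 85.9%, 79.8% and 67.8% as printed, and 80–82% centred. A vague intercept prior gives Type 1 error of 4.5–6.0% in all 12 settings, with power 76–79%.

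These fits use a normal approximation at the posterior mode. Importance sampling of the exact posterior on 400 data sets agreed: 15.5% against 15.8% at slope -0.2, and 9.5% by both at -0.1. With baseline mean 14.4 instead, the printed code gives 15.2%, 8.7%, 4.7% and 2.4%.

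**5. The primary model, with 45 random centres** (2,000 trials per setting, SoC 45%). At centre variance 0.10: 15.7%, 8.8%, 4.9% and 2.6% as printed; 4.4–4.6% centred. At variance 0.25 and slopes -0.2 and -0.1: 13.8% and 8.6% as printed; 4.5% and 4.0% centred.

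**6. Which slope is plausible.** ACT is an integer and entry is 18 or less. For a baseline of 17 or less, reaching 20 already means a gain of at least 3, so the ≥20 limb adds responders only at baseline 18. Response is almost exactly a gain of 3 or more, which falls with baseline whenever Week 24 ACT regresses on baseline with a coefficient below 1. Generating Week 24 ACT directly (residual SD 3.0–4.5, assumed):

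| Regression coefficient | Implied slope | Type 1 error, printed |
|---|---|---|
| 0.5 | -0.25 to -0.17 | 18.5–13.1% |
| 0.7 | -0.14 to -0.10 | 11.2–9.3% |
| 0.9 | about -0.03 | 5.1–6.7% |

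Centred, it is 4.0–5.2% throughout.

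**The case against.** The strongest reply is that the harm rests on a slope the documents do not give. With slope 0 and SoC 45% the printed code behaves as designed, a positive slope makes it conservative, and a regression coefficient of 0.9 gives only 5.1–6.7%. This stands as a limit on size and direction, not on the mechanism.

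Second, centring is not uniformly closer to 5%. Of the 12 null settings, centring is closer in six, the printed code in four, and two tie; at SoC 60% the centred model still has 9.2–11.4%. This also stands. The residual error is the intended prior's own behaviour, close to the design's 1.9% and 9.3% at SoC 30% and 60%. Where the printed code does better, it does so because the intended prior has been disabled.

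Third, y0 might already be centred in the analysis data set. The SAP does not say so, and its formula names the baseline ACT value itself; if centring is meant, it must be written down.

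Fourth, SAP 2.4 warns that power and Type 1 error vary and points to a figure not available here, and SAP 7 says there is no hypothesis testing. But SAP 6.2.2 states hypotheses, and SAP 2.4 promises a 5% error rate.

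Finally, sensitivity analysis 1 is free of the prior, so a large shift might show there. It also changes the missing-data handling and drops the centre effect, so it could not be attributed to the prior.

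**Conclusion.** The primary analysis is wrong as written. That the prior acts at ACT 0, and that item 4 contradicts the code, follow from the text alone. The size is conditional. At SoC 45% and slopes of -0.1 to -0.2, Type 1 error is about 9–16% instead of 5%, with null odds ratios inflated by about 7–14% (exp(0.07) = 1.07, exp(0.13) = 1.14). At slope +0.1 it is about 2–3% and power falls to about 68%. At slope 0 there is no material harm. These figures rest on the assumed slope, baseline ACT distribution, residual SD and centre variance. The more plausible direction favours the DS. The 5% and 78% in SAP 2.4 do not generally carry over to the coded model.

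**What to change.** - In the code of SAP 6.2.2 and of sensitivity analysis 2 in SAP 6.2.3, replace y0 by baseline ACT minus the mean baseline ACT pooled over both arms, and show this in the model formula. SAP 6.2.4 then follows by reference. The intercept becomes the SoC logit at average baseline, close to what the Beta prior describes.
- Correct item 4 in SAP 6.2.2: the informative prior is on the intercept (SoC rate) and the treatment prior is vague. Explain the difference from Protocol 9.5.4.1.
- Add one run of the same random-centre model with a vague intercept prior, so that the prior's influence can be seen alone. This is also the version that holds Type 1 error near 5% across SoC 30–60%.
- Restate in SAP 2.4 the Type 1 error and power of the coded model over SoC 30–60%.

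The cost is one changed term in two programs, a few sentences, one extra model run and one simulation table. SAP 2.5.2 allows amendments before database lock, and trial conduct is unaffected.

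### SAP 6.2.2 specifies the primary model at two incompatible units, patient and arm-by-centre total, and leaves the level and scale of the baseline ACT term undefined

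*SAP*

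**What the plan says.** SAP 6.2.2 describes the primary model three times.

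- **Estimand text, items 2 and 4.** Each patient is a responder or a nonresponder, and the "binary variable responder rate (Yes/No) will be modeled through logit link function, with baseline ACT score and treatment as explanatory factors". This is a patient-level model.
- **Equation.** The modelled quantity is p_ij, the response proportion of arm i at centre j. There is a random centre term but no patient index, although baseline ACT is on the right-hand side.
- **Code.** The likelihood line is "model count ~ binomial(n = total, p = pi"), and the note beneath the code reads "where count = number of responders and total = number of patients". The covariate is `y0`, used without centring. The SAP does not say whether it is a patient's value or a summary, or what one row of data set `x` represents.

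Sensitivity analysis 2 in 6.2.3 repeats the likelihood line and the note. The Week 12 analysis in 6.2.4 inherits them by cross-reference. Sensitivity analysis 1 is different: it derives the response for each patient and regresses `y` on treatment and `actbase`, and the SAP calls this the model for the primary endpoint.

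**The concern.** A programmer who follows the equation and the note would build one row per arm and centre. Such a row cannot hold the baseline ACT of each of its patients, so `y0` would have to be a cell summary, most naturally a mean. Part of the responder rule is a change from the patient's own baseline, and baseline ACT is the only patient covariate in the model. Replacing it by a cell mean discards most of its variation.

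Three things are at stake. The primary result would depend on a data layout that the SAP does not state. Some power from the covariate could be lost. Sensitivity analysis 1 would also differ from the primary analysis in the level of the covariate, not only in its handling of missing data, its priors and the centre effect. The protocol cannot settle the matter, because the SAP says that it prevails where the two differ.

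**Working it through.** **1. The plan's own figures (SAP 2.4).** Inputs: "With assumptions of response rates of 58% and 45% for the DS and SoC groups"; "200 patients in the DS group and 150 patients in the SoC group, to be available for analysis"; one-sided 5%.

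- Pooled rate = (200 × 0.58 + 150 × 0.45)/350 = 0.5243.
- Null SE = √[0.5243 × 0.4757 × (1/200 + 1/150)] = 0.0539.
- Alternative SE = √(0.58 × 0.42/200 + 0.45 × 0.55/150) = 0.0536.
- z = (0.13 − 1.645 × 0.0539)/0.0536 = 0.77, so power is 78.0%, as stated.
- Exact enumeration of both binomials with Beta(9.52, 11.88) for SoC and Beta(0.5, 0.5) for DS gives a 81.7% chance that P(OR>1) is at least 0.95. The SAP says about 82%.

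Neither figure includes a baseline covariate, so neither depends on the point at issue.

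**2. What a cell mean retains.** With about 45 centres (Protocol 3.2), a cell holds 200/45 = 4.4 DS or 150/45 = 3.3 SoC patients. There are 90 cells. If baseline ACT does not differ systematically between centres, cell means carry about 89/349 = 26% of its variation.

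**3. Success probability, planned priors, ACT centred.** The documents give neither the ACT-response slope nor the ACT SD, so both are assumed: baseline ACT about normal(14, 3), rounded and clipped to 5–18 (SD 2.8). Other settings: 44 centres, no centre effect, normal approximation to the posterior, 10,000 trials per slope.

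| Slope per ACT point | No ACT | Patient's ACT | Cell-mean ACT | Points lost | Share of gain lost |
|---|---|---|---|---|---|
| -0.20 | 82.0% | 84.9% | 83.1% | 1.8 | 1.8/2.9 = 62% |
| -0.25 | 82.2% | 85.8% | 83.6% | 2.2 | 2.2/3.6 = 61% |
| -0.30 | 81.8% | 86.8% | 84.0% | 2.8 | 2.8/5.0 = 56% |

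A rerun with 45 centres and 6,000 trials per slope gave losses of 1.5, 1.8 and 2.8 points at these slopes (84.1 v 82.6%, 85.3 v 83.5%, 86.4 v 83.6%). At -0.1 the loss was about 0.4 to 0.6 points.

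**4. Cross-check, flat priors, slope per SD of ACT (SD about 2.5), 30,000 trials each.** Columns are no ACT / patient's ACT / cell mean.

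- 0.5: 77.7 / 79.8 / 78.4%. Loss 1.4 of 2.1 points (67%).
- 0.75: 77.8 / 81.8 / 79.3%. Loss 2.5 of 4.0 points (61% before rounding).
- 1.0: 77.6 / 84.2 / 80.8%. Loss 3.4 of 6.6 points (51% before rounding).

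With a random centre effect (SD 0.5, treated as known) and slope 0.5, the share lost was about 56% (2,000 trials). Type 1 error with cell means did not exceed that of the other two analyses, and fell to about 4% at slope 1.0.

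**5. The scale of `y0`.** The code gives beta0 a Normal(-0.231, 0.192) prior, converted from the SoC Beta prior. With raw ACT, beta0 is the SoC log-odds at ACT = 0, below the scale minimum of 5. Suppose the slope is -0.2, mean ACT is 14, and SoC response is 45% at the mean. The intercept consistent with this is ln(0.45/0.55) + 0.2 × 14 = 2.6, which lies (2.6 + 0.231)/√0.192 = 6.5 prior SDs from the prior mean. The fit compromises partly by raising beta1. Simulated one-sided type 1 error at 45% in both arms:

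| Slope | Raw patient ACT | Raw cell mean | Centred, either layout |
|---|---|---|---|
| -0.1 | about 11% | about 7% | 4–5% |
| -0.2 | about 16% | about 8% | 4–5% |
| -0.3 | about 24% | about 9% | 4–5% |

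**The case against.** The strongest reply is that the code does not force aggregation. A binomial likelihood with a total of 1 is the patient-level logistic model, and one row per centre, arm and ACT value gives the same likelihood up to a constant. Under either layout nothing is lost. The SAP nowhere mentions averaging baseline ACT, and both the estimand text and sensitivity analysis 1 point to patients as the unit. This stands. A reader might infer that the SAP prescribes a cell-mean adjustment, but the documents do not support that. It is one way to fill an undefined variable.

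It is also fair that the loss is small and rests on assumed slopes, that cell-mean success in the first table (83.1% to 84.0%) remains above the planned figure of about 82%, and that the imprecise ACT slope is a nuisance parameter.

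What does not stand is the suggestion that nothing needs changing. The equation and the note both describe grouped totals, and a number of patients is an odd definition for a constant 1.

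**Conclusion.** The SAP contradicts itself on the unit of its primary model, so the analysis cannot be reproduced from the text as it stands. If the code is run on arm-by-centre totals, the cost is roughly 0.4 to 3 points of success probability for slopes of -0.1 to -0.3 per ACT point with ACT centred. That is about half to two thirds of the covariate gain at the stronger slopes. If rows are patients, the cost is zero. The figures rest on an assumed slope and ACT distribution, near-equal centre sizes, and a normal approximation in place of MCMC. Most runs had no centre effect.

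Two stronger conclusions are tempting and unsupported. Grouping does not leave the trial short of its stated power, because the 78% and 82% assume no covariate. Nor does grouping inflate type 1 error. The inflation in step 5 comes from setting an informative intercept prior against uncentred ACT. It arises in both layouts and is larger with patient rows. A patient-level rewrite is therefore sound only with centred ACT.

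**What to change.** Before database lock, amend SAP 6.2.2 as follows.

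1. Index the equation by patient: y_ijk ~ Bernoulli(p_ijk), with logit(p_ijk) = beta0 + beta1·x_i + beta2·(ACT_ijk − mean ACT) + Center_j.
2. State that data set `x` has one record per mITT patient, with either a binary outcome or `count` 0/1 and `total` 1. The existing likelihood line can then stay.
3. Define `y0` as the patient's own baseline ACT minus the overall mean, so that the beta0 prior from Beta(9.52, 11.88) applies at average ACT.
4. Make the same change in sensitivity analysis 2 of 6.2.3, and confirm that 6.2.4 inherits it.

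Item 3 must accompany items 1 and 2: patient rows with uncentred ACT should not be adopted under these priors. The cost is SAP wording, one derived variable and at most one changed code line. No new data are needed. If patient rows were always intended, the change records that and fixes the scale of `y0`.
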